#### Contraception

17. Agreement by WOCBP **and** males of childbearing potential\* to use an adequate method of birth control (hormonal contraception is inadequate) or abstain from heterosexual activity for the course of the study through 90 days after the last dose of protocol therapy.

\*Childbearing potential defined as not being surgically sterilized (men and women) or have not been free from menses for > 1 year (women only).

### 3.2 Exclusion Criteria

#### Previous therapies

- 1. Bcl2 inhibitors
- 2. Any systemic anti-lymphoma therapy, including monoclonal antibody within 28 days or 5 half-lives (whichever is shorter) of initiating protocol therapy
- 3. Radiation and/or surgery (except lymph node or other diagnostic biopsies) within 14 days prior to Day 1 of protocol therapy.
- 4. Short course systemic corticosteroids for disease control, improvement of performance status or non-cancer indication within 7 days prior to Day 1 of protocol therapy. Stable ongoing corticosteroid use (i.e. at least 30 days) up to an equivalent dose of 20 mg of prednisone is permissible.
- 5. Strong or moderate CYP3A inhibitors within 7 days prior to Day 1 of protocol therapy.
- 6. Strong or moderate CYP3A inducers within 7 days prior to Day 1 of protocol therapy.
- 7. P-gp inhibitors within 7 days prior to Day 1 of protocol therapy.

\_\_\_8. Narrow therapeutic index P-gp substrates within 7 days prior to Day 1 of protocol therapy.

\_\_\_9. Any other investigational agent or used an investigational device within 21 days prior to Day 1 of protocol therapy.

Other illnesses or conditions

\_\_\_10. Prior surgery or gastrointestinal dysfunction that may affect drug absorption (e.g., gastric bypass surgery, gastrectomy)

\_\_\_11. Active human immunodeficiency virus (HIV) or hepatitis C virus (HCV) or hepatitis B virus (HBV). Subjects who have an undetectable HIV viral load with CD4 > 200 and are on HAART medication are allowed. Subjects who are positive for hepatitis B core antibody or hepatitis B surface antigen must have a negative polymerase chain reaction (PCR) result before enrollment. Those who are PCR positive will be excluded. Patients who have had Hepatitis C but have finished treatment and are PCR negative will be allowed. (Testing to be done only in patients suspected of having infections or exposures).

\_\_\_12. Concurrent malignancy requiring active therapy.

\_\_\_13. Known central nervous system or meningeal involvement (in the absence of symptoms, investigation into central nervous system involvement is not required).

\_\_\_14. Congestive heart failure (CHF) that meets New York Heart Association (NYHA) Class II to IV definitions (See [Appendix E](#)).

\_\_\_15. Patients with known cardiac abnormalities such as:

- Congenital long QT syndrome
- QTc (Corrected QT interval on ECG) interval >480 milliseconds
- Any cardiac arrhythmia requiring anti-arrhythmic medication.

\_\_\_16. Patients with a history of sustained ventricular tachycardia (VT), ventricular fibrillation (VF), Torsade de Pointes, or cardiac arrest, unless currently addressed with an automatic implantable cardioverter defibrillator (AICD).

\_\_\_17. Active infection requiring systemic therapy.

\_\_\_18. Unable to swallow capsules, has a partial or small bowel obstruction, or has a gastrointestinal condition resulting in a malabsorptive syndrome (e.g. small bowel resection with malabsorption).

\_\_\_19. WOCBP: Pregnant or breastfeeding.

\_\_\_20. Any other condition that would, in the Investigator's judgment, contraindicate the patient's participation in the clinical study due to safety concerns with clinical study procedures.

Noncompliance

\_\_\_21. Prospective participants who, in the opinion of the investigator, may not be able to comply with all study procedures (including compliance issues related to feasibility/logistics).

Eligibility Confirmed* by (Choose as applicable):	Print Name	Signature	Date
 Site PI			
 Authorized study MD			
 Study Nurse			
 Study CRA/ CRC			
 Other: _____			

\*Eligibility should be confirmed per institutional policies.

## 4.0 PARTICIPANT ENROLLMENT

---

**NOTE: Sites must meet activation requirements prior to enrolling participants.**

### 4.1 Pre-Enrollment Informed Consent and Screening Procedures

Diagnostic or laboratory studies performed exclusively to determine eligibility will be done only after obtaining written informed consent. Studies or procedures that are performed for clinical indications (not exclusively to determine study eligibility) may be used for baseline values and/or to determine pre-eligibility, even if the studies were done before informed consent was obtained. The informed consent process is to be fully documented (see [Section 16.4](#)), and the prospective participant must receive a copy of the signed informed consent document. Screening procedures are listed in [Section 10.0](#).

### 4.2 Participant Enrollment

Eligible participants will be registered on the study centrally by the DCC at City of Hope. DCC staff are **available between the hours of 8:00 a.m. and 5:00 p.m. PST, Monday through Friday (except holidays)**. DCC contact information is as follows:

- [contact]
- E-mail: [[contact]](mailto:[contact])

### 4.3 Slot verification and reservation

Once the Safety Lead-in is completed and the proposed dose and schedule is shown to be tolerable, participants will enroll at the tolerable dose and schedule (which includes the ramp-up stage) ([Section 5.3](#)).

Issues that would cause treatment delays should be discussed with the Principal Investigator.

Designated study staff should call the DCC to verify current slot availability, and to reserve a slot for a specific prospective subject. Slots can only be held for a limited time.

The DCC should be notified of cancellations of prospective participants holding slots as soon as possible.

### 4.4 Registration Process

To register a participant, the subsequent procedure is to be followed.

1. The participating site's data manager/coordinator/research nurse should contact the DCC via telephone or email to provide notification regarding the pending registration and communicate desired timeline of the registration, especially if it must be completed promptly to meet the registration window.
2. The data manager/coordinator/research nurse should then e-mail copies to [[contact]](mailto:[contact]) of the following documents to the DCC:
  - Registration Cover Sheet ([Appendix H-1](#))
  - Completed Eligibility Criteria List (printed from [Section 3.0](#) of the protocol)
  - Source documentation to support eligibility criteria\*\*
  - Signed informed consent document
  - Signed HIPAA authorization form (if separate from the informed consent document)
  - Signed subject's Bill of Rights (COH only)

\*\*For COH participants, provide copies of source documentation only if not readily available as a finalized record in a COH Electronic Medical Record (EMR).

3. After having received all transferred documentation, the DCC will complete the review the documents to verify eligibility, working with the participating site as needed to resolve any missing required source elements. A participant failing to meet all protocol eligibility requirements will not be registered.
4. Once eligibility has been confirmed, DCC staff will register the participant by: assigning a subject accession number, register the subject on study centrally into COH clinical trials management system for non-COH participants, and enter the participant into the eCRF system, Medidata RAVE.
5. Once registration has been completed, DCC staff will send a Confirmation of Registration Form within 24 hours, including the participant study number to:
  - The study team: Site Lead Investigator, treating physician, protocol nurse, CRC and pharmacy
  - The COH sponsor team designees

#### **4.5 Screen Failures and Registered Participants Who Do Not begin Study Treatment**

The DCC is to be notified of all participants who sign consent but do not meet eligibility criteria or do not initiate protocol therapy. For non-COH sites, the reason for screen failure will be documented in registration coversheet (see [Appendix H-1](#)) and submitted to the DCC.

### **5.0 TREATMENT PROGRAM**

---

#### **5.1 Treatment Program Overview**

This is a multi-center, open-label, single-arm Phase 2 trial of venetoclax with romidepsin for patients with relapsed/refractory mature T-cell lymphoma.

The study consists of a Safety Lead-in stage to evaluate safety/tolerability and a Phase 2 stage to evaluate anti-tumor activity in the study population ([Section 5.3](#)). Participants will receive up to 26 cycles of therapy and each cycle will be 28 days.

Protocol treatment will continue until disease progression, unacceptable toxicities, completing 26 cycles of therapy, or meeting other [Section 5.7](#) criteria, whichever comes first. If a patient is still benefiting from treatment at the completion of 26 cycles of therapy, we will consider amending the study to extend the duration of therapy for that particular patient.

During Cycle 1, all participants will be monitored closely for tumor lysis syndrome (TLS, [Section 5.9.2](#)).

Participants who discontinue protocol therapy will undergo follow-up (see [Section 5.8](#)). Windows for all assessments and treatments are detailed in [Section 10.0](#).

#### **5.2 Treatment Cycle Definition**

The treatment cycle will be a fixed 28 days (**Note:** exceptions due to unusual operational considerations may be permitted as described in [Section 6.2](#)).

[figure not shown]
The cycle day count and cycle count will continue despite a hold in venetoclax or romidepsin administration due to toxicities (See [Section 6.2](#)) - i.e. a cycle may initiate even if either drug is being held.

Cycle 1 Day 1 is defined as the first day of venetoclax and romidepsin administration.

### 5.3 Treatment Plan

Participants will ramp-up daily over the first week of Cycle 1 to the maximum venetoclax dose. From Cycle 1 Days 8-28 and Cycle 2+ Days 1-28, participants will continue at the maximum dose (Figure 5.3) of venetoclax. Romidepsin 14 mg/m^2 will be administered on days 1, 8, and 15 of each cycle.

**Figure 5.3. Dosing Schedule**

#### 5.3.1 Safety Lead-in

During the safety-lead in, 6 evaluable participants will be enrolled using a 3+3 design. Unacceptable toxicities are defined in [Section 11.2](#) and will be evaluated during the first 2 cycles of therapy.

In the event the proposed dose (20-800 mg/day) of venetoclax plus romidepsin is not tolerable (2+ participants with unacceptable toxicity in ≤ 6 evaluable participants), the accrual will be suspended and the study will be amended.

#### 5.3.2 Phase 2

Once the Safety Lead-in is completed and the proposed dose is shown to be tolerable, additional patients will be enrolled and treated for the Phase 2 response evaluation. A Simon 2-stage optimal design will be utilized. Patients enrolled during the Safety Lead-in will be included in the Phase 2 portion of the study if they are evaluable for response. In the absence of study holds to accrual for toxicity or for futility, accrual will continue until 18 evaluable participants are treated.

See [Section 12.0](#) for details.

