### **11.2 Unacceptable Toxicity During Safety Lead-In**

Unacceptable toxicity will be defined as one of the following AEs that is **at least possibly related** to either venetoclax or romidepsin treatment within the first 2 cycles of protocol therapy:

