#### 12.1.1 Safety Lead-In

Prior to formally initiating the Phase 2 response evaluation, a patient Safety Lead-in will be conducted to ensure the proposed treatment is tolerable. Up to 6 evaluable patients may be enrolled in two cohorts of 3 patients each at the proposed venetoclax dose (maximum dose of 800 mg/day with a 1-week dose ramp up schedule) plus romidepsin as outlined below. Initially up to 3 evaluable patients can be enrolled and treated. After 3 patients are treated and evaluated for unacceptable toxicities, if 0/1 out of 3 evaluable patients experience unacceptable toxicities during the first 2 cycles, up to 3 additional patients will be enrolled and treated to bring the total number of patients treated to 6. If  $\leq 1/6$  evaluable patients experience unacceptable toxicities during the first 2 cycles, the proposed treatment dose/schedule (including ramp-up) will be considered tolerable and be used for the subsequent Phase 2 response evaluation. At any time during the Safety Lead-in, if  $\geq 2$  patients experience unacceptable toxicities during the first 2 cycles, the accrual will be suspended and the study will be amended. The unacceptable toxicities are defined in [Section 11.2](#). Unacceptable toxicities will be evaluated during the first 2 cycles of therapy to ensure monitoring of participants during the venetoclax ramp-up period (Cycle 1) and while participants are on steady-state venetoclax dose (Cycle 2). Patients inevaluable for unacceptable toxicities during the Safety Lead-in will be replaced (see below in [Section 12.3](#)).

#### 12.1.2 Phase 2

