The Phase 2 response evaluation will accrue a minimum of 7 evaluable patients and a maximum of 18 evaluable patients. Patients enrolled during the Safety Lead-in period of the study (n=6) will be included in the Phase 2 response evaluation provided that they are evaluable for response (defined in [Section 12.3](#)). The response evaluation will be based on a Simon's Two-Stage Optimal design [53], to distinguish a promising 30% response rate (alternative hypothesis) from a disappointing rate (null hypothesis) of 10%, at a one-sided type I error of 10% and a power of 80%. In the first stage, 7 evaluable subjects will be accrued. If there is 0 response among the 7, the study accrual will be suspended. If there are 1 or more responses among the 7, the study will remain open to accrue a total of 18 evaluable patients. Observing 4 or more responses among 18 evaluable patients will reject the null hypothesis and indicate the response rate being promising in this study setting. Observing 3 or fewer responses among 18 evaluable patients will fail to reject the null hypothesis and will not establish efficacy of the treatment.

For the purpose of the 1st stage response evaluation, study accrual may be temporarily suspended until all Stage 1 enrollments are assessed for response after at least 4 cycles of treatment or are otherwise off-treatment. If by that time no responders have been observed, the study accrual will be terminated. On

the other hand, if at least one responder has been observed prior to enrolling the 7th patient for Phase II, then Phase II accrual will continue directly to Stage 2 without interruption.

If no toxicity is noted at the proposed dose/schedule and there is no efficacy either, the protocol may be amended after discussion with the industry partner to increase the maximum dose of venetoclax up to 1200 mg/day.

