### **12.2 Accrual and Expected Duration of Trial**

The expected sample size for the Phase 2 response evaluation is 18 patients evaluable for response (assuming the response evaluation passes the first stage). Patients enrolled during the Safety Lead-in of the romidepsin/venetoclax combination will be included in the Phase 2 response evaluation if they are evaluable for response which requires a response evaluation after 2 cycles. We expect that all patient enrolled during safety lead-in will have a response evaluation after 2 cycles. Therefore, the total sample size for the study including the Safety Lead-in is expected to be 18 evaluable patients. Assuming approximately 10% of the patients need to be replaced for safety lead-in or Phase 2 evaluation, the maximum sample size for evaluating the combination of venetoclax and romidepsin is 20 patients.

The 6 patients enrolled on the previous versions of protocols with single agent venetoclax will be analyzed separately and excluded from the main analyses which evaluate the combination of venetoclax and romidepsin. Therefore, the maximum sample size of the study will be 26 accounting for these 6 prior enrollments.

City of Hope saw ~160 PTCL patients per year, with ~30 new patients per year (mix of newly diagnosed and relapsed or refractory). This will be a multicenter study with 3 total sites. We expect a total accrual of 1-2 patients per month across all sites. Therefore, accrual is expected to be completed in 24 months.

Participant duration is planned for 4 years which includes maximum time for treatment (24 months) and expected post-treatment follow-up (24 months). The estimated total study duration will be 6 years, with 2 years of accrual and approximately 4 years of treatment and follow-up for the last patient.

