## 12.4 Stopping Rules for Tumor Lysis Syndrome (TLS)

Besides prophylaxis and dose modification for TLS per [Section 5.9.3](#) and [Section 7.2](#), the study will implement accrual stopping rules for both clinical TLS and laboratory TLS. When a stopping rule is triggered, the study PMT will review and assess the safety of the trial and submit a report to the COH DSMC. The COH DSMC will review for approval any decision to continue or permanently suspend accrual to the trial.

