### **16.3 Protocol Management Team (PMT)**

The Protocol Management Team (PMT), minimally consisting of the study PI, site investigators, collaborating investigators, research nurse, clinical research associate/coordinator, and the study

biostatistician, is responsible for ongoing monitoring of the data and safety of this study, including implementation of the stopping rules for safety/toxicity.

The PMT is recommended to meet (in person or via teleconference) at least monthly to review study status. This review will include, but not be limited to, reportable AEs and UPs, and an update of the ongoing study summary that describes study progress in terms of the study schema. The meeting will be a forum to discuss study related issues including accrual, SAE/AEs experienced, study response, deviations/violations and study management issues. The appropriateness of further subject enrollment and the specific intervention for subsequent subject enrollment are addressed. It is recommended that minutes of these discussions be taken to document the date of these meetings, attendees and the issues that were discussed (in a general format).

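### After the six-patient lead-in, the only pre-specified toxicity rules for accrual are for tumor lysis syndrome; other unacceptable toxicity in about 12 of 18 patients has no numeric boundary

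*Combined protocol and SAP*

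**What the plan says.** Section 5.3.2, with parallel text in Section 2.7 and the synopsis, makes accrual to full size conditional: "In the absence of study holds to accrual for toxicity or for futility, accrual will continue until 18 evaluable participants are treated". It sends the reader to Section 12.0 for details.

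The rules that could produce a toxicity hold are these:

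- **Lead-in rule.** Section 12.1.1 introduces its limit of two patients with "At any time during the Safety Lead-in, if". Section 5.3.1 states the same limit: "2+ participants with unacceptable toxicity in ≤ 6 evaluable participants), the accrual will be suspended and the study will be amended". The events are defined under the heading "Unacceptable Toxicity During Safety Lead-In" (Section 11.2) and are counted in the first two cycles.
- **TLS rules.** Section 12.4 says "the study will implement accrual stopping rules for both clinical TLS and laboratory TLS". The first clinical TLS suspends accrual. So does laboratory TLS in 1 patient with up to 5 treated, in 2 with up to 14 treated, or in 3 at any point.
- **Phase 2 rule.** Section 12.1.2 gives only the futility rule (0 responses in 7).

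Section 16.3 makes the PMT responsible for monitoring, "including implementation of the stopping rules for safety/toxicity". On numbers, Section 12.1.2 says "Patients enrolled during the Safety Lead-in period of the study (n=6) will be included in the Phase 2 response evaluation", on condition that response can be assessed in them. Section 12.2 adds: "We expect that all patient enrolled during safety lead-in will have a response evaluation after 2 cycles".

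**The concern.** The plan leans on toxicity holds throughout Phase 2, yet the boundary for unacceptable toxicity lapses once the lead-in ends. From then on, a run of non-TLS events that would have suspended the lead-in reaches no stated limit.

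This matters because the combination is new. Section 2.6 offers laboratory evidence of synergy for venetoclax with romidepsin, and the documents report no clinical safety data for the pair. The six earlier enrollments received venetoclax alone (Section 12.2). Section 6.1 lists neutropenia, thrombocytopenia and anemia as very common with each drug, so shared marrow toxicity is foreseeable, and TLS rules will not detect it. The data for a rule are already collected: all toxicity grades are recorded in Cycles 1-2 (Section 11.1), and characterizing toxicity is a Phase 2 secondary objective (Section 1.2).

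**Working it through.** **1. The plan's own figures.** For the Simon design (0/7, then at least 4/18; 10% versus 30%), exact enumeration gives a type I error of 0.089 and power of 0.800, as stated. The replacement allowance gives 18/(1 − 0.10) = 20, also as stated. Patients after the lead-in: 18 − 6 = 12 evaluable, or up to 20 − 6 = 14 treated if all replacements fall in Phase 2.

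**2. How well the lead-in screens.** The documents give no true toxicity rate, so p is an assumption and a range is shown. The chance of passing is P(at most 1 of 6) = (1−p)^6 + 6p(1−p)^5.

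- p = 0.30: 0.1176 + 0.3025 = 0.420
- p = 0.40: 0.0467 + 0.1866 = 0.233
- p = 0.50: 0.0156 + 0.0938 = 0.109

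A result of 1/6 has a two-sided 95% Clopper-Pearson upper limit of 64%.

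**3. What may follow.** Expected events in the next 12 patients are 12p: 3.6 at 30% and 4.8 at 40%. The chance of passing the lead-in and then seeing at least 4 events in those 12 is 0.420 × 0.507 = 21% at 30%, and 0.233 × 0.775 = 18% at 40%. Unless the events are TLS, no written boundary responds.

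**4. An example boundary.** Count Section 11.2 events in Cycles 1-2 from the first lead-in patient. Suspend accrual for review at 3 events with up to 9 treated, 4 with up to 12, 5 with up to 15, or 6 with up to 18. Start from 0 or 1 events in 6, given that the lead-in was passed. For patients 7 to 18 apply f_i(k) = f_{i−1}(k)(1−p) + f_{i−1}(k−1)p, and move any probability at or above the boundary to a hold. The unconditional figure is the conditional one times the chance of passing.

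| True rate | Passes lead-in | Hold, given pass | Hold, unconditional |
|---|---|---|---|
| 15% | 0.776 | 5.6% | 4% |
| 20% | 0.655 | 12.7% | 8% |
| 30% | 0.420 | 35.5% | 15% |
| 40% | 0.233 | 62.7% | 15% |
| 50% | 0.109 | 84.1% | 9% |

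**5. Patients treated.** Given a pass, and before any futility stop, the mean number treated (maximum 18) is 13.8 at 40% and 12.0 at 50% if each outcome were known at once. It is not: the window is 2 × 28 = 56 days, and Section 12.2 expects 1-2 patients per month, so about 2 to 4 more could enroll meanwhile. With 2 to 4 patients added at each hold, capped at 18, the means become about 15 to 16 at 40% and 13.6 to 15 at 50%.

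**The case against.** The strongest reply is that Phase 2 toxicity is overseen. Section 16.3 recommends PMT meetings at least monthly that consider whether enrollment should go on. Section 16.6 gives the DSMC a report every 3 months and a vote on study status. Section 14.3.2 requires serious events during treatment, or within 30 days after it, to be reported within 24 hours. All of this stands. What is missing is a pre-specified boundary, not monitoring. Even so, the plan did not leave TLS or the lead-in to judgment alone, and it gives no reason to treat other toxicity differently.

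Three stronger readings are tempting, and the documents do not support them:

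- **A reader might infer that the reference to toxicity holds is empty in Phase 2, or that any Section 11.2 event can accumulate freely.** Clinical TLS is itself a Section 11.2 event and suspends accrual at the first case throughout the study. Laboratory TLS is bounded throughout as well. This is a gap in a design choice, not a contradiction.
- **A reader might infer that a hold for other toxicity is impossible.** Only an automatic numeric hold is. The committees can stop accrual by judgment.
- **A reader might take 62.7% and 84.1% as the overall gain, or expect the trial to shrink from 18 to 13.8 or 12.0 patients.** Those probabilities are conditional on passing the lead-in; the unconditional gains are about 15% and 9%. The smaller sample sizes assume no evaluation lag. Futility stopping also already lowers the expected size, to 12.7 at a 10% response rate and 17.1 at 30%.

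It is also fair to say that the example misses almost two-thirds of trials with a 30% true rate that pass the lead-in, and that the documents set no acceptable rate from which to derive a boundary.

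**Conclusion.** The concern holds in a limited form. After the lead-in, non-TLS unacceptable toxicity in about 12 of 18 patients (up to 14 of 20 treated) has no pre-specified accrual boundary, although Sections 2.7 and 5.3.2 rely on toxicity holds. The lead-in alone lets a 30% true rate through 42% of the time and a 40% rate 23% of the time. A simple trigger would add a guaranteed review, with a moderate chance of acting at 30% and a good chance at 40% or more once the lead-in is passed.

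This rests on assumed true rates, independent patients with a constant risk, and all six lead-in patients being evaluable for response, as Section 12.2 expects. The example probabilities are computed to 18 patients. This is a worthwhile, inexpensive improvement to patient safety; it does not show that the trial is unmonitored.

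**What to change.** First reconcile the event definition. The synopsis counts Grade 4 thrombocytopenia with bleeding that needs transfusion, whereas Section 11.2 counts Grade 3 or 4. A continuing rule needs one definition, and the sponsor must decide which.

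Then, in Section 12.4 and the matching stopping-rule text of the synopsis:

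- Apply the Section 11.2 events in Cycles 1-2 to all treated patients, counting from the first lead-in patient.
- Suspend accrual for PMT and DSMC review, by the process already used for TLS, at a cumulative boundary. An example is 3 events with up to 9 treated, 4 with up to 12, 5 with up to 15 and 6 with up to 18, extended to the maximum of 20.
- Have the sponsor confirm the acceptable rate, and print the operating characteristics of the final boundary.
- Adjust the headings of Sections 11.2 and 12.4. State in Section 12.3 who counts in Phase 2, since toxicity evaluability is now defined only for the lead-in.

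If the sponsor prefers no boundary, Sections 2.7 and 5.3.2 should say that Phase 2 toxicity holds mean the TLS rules plus committee judgment.

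The cost is a short set of text edits and, with the example, about a 6% chance of an unnecessary review pause at a true rate of 15% and 13% at 20%, given a passed lead-in. It is a trigger for review of accrual and changes no patient's treatment.
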